4.8.2 Analysis Populations

The Intent-to-treat population will include all subjects who receive any investigational product analysed according to randomised treatment group.

The Modified Intent-to-treat (mITT) population will include all subjects who receive at least one dose of investigational product in the double-blind treatment period analysed according to randomised treatment group.

The As-treated population will include all subjects who receive any investigational product analysed according to the treatment they actually receive.

The Per-protocol population will include all subjects in the mITT population who complete treatment with investigational product up to Day 58.

The PK population will include all subjects in the As-treated population and have at least one PK sample taken that is above the lower limit of quantitation.

The Immunogenicity population will include all subjects in the As-treated population who have at least one serum sample for immunogenicity testing.

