3.1.4.3 Hyperglycaemia

In the event of suspected persistent hyperglycaemia in a subject based on either symptoms of hyperglycaemia (eg, thirst, polyuria, blurred vision) or capillary plasma glucose readings (eg, 3 readings > 14 mmol/L [260 mg/dL] within 1 week), the investigator should perform additional fasting blood glucose level tests as necessary. If 2 or more laboratory plasma fasting glucose levels of > 14 mmol/L (260 mg/dL) more than 3 days apart are detected, the investigator should consider rescue therapy following discussion with the medical monitor.

In the unlikely event that a subject is unwell and severe persistent hyperglycaemia (eg, fasting glucose > 14 mmol/L [260 mg/dL]) is suspected by the investigator, the subject should be advised to monitor capillary plasma glucose levels up to 5 times per day and rescue therapy should be administered within a 24- to 48-hour time frame if required.

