4.1.6 Discontinuation of Investigational Product

An individual subject will not receive any further investigational product if any of the following occur in the subject in question:

- 1 Withdrawal of consent from further treatment with investigational product
- 2 Lost to follow-up
- 3 An AE that, in the opinion of the investigator or the sponsor, contraindicates further dosing: specific examples include:
 - Dose-limiting symptoms with respect to GI tolerability and in particular if a subject requires intravenous fluids for more than 48 hours to treat volume depletion

secondary to nausea and vomiting, even after measures are taken to reduce the risk of vomiting, after discussion with the medical monitor

- Any subject where Hy's law criteria on liver function tests is met: AST or ALT $\geq 3 \times$ ULN **together with** total bilirubin $\geq 2 \times$ ULN
 - Any subject who develops a life-threatening arrhythmia including sustained ventricular tachycardia, ventricular fibrillation or new ECG changes of second or third-degree heart block
 - Subjects with persistent fasting glucose level of > 260 mg/dL (14.4 mmol/L) despite a maximum tolerated dose of rescue therapy to enable optimisation of the subject's glycaemic control
- 4 Subject noncompliance that, in the opinion of the investigator or sponsor, warrants withdrawal (eg, refusal to adhere to scheduled visits)
 - 5 Pregnancy in a female subject

Subjects who are permanently discontinued from receiving investigational product will be followed for protocol-specified assessments including follow-up of any AEs unless consent is withdrawn from further study participation (Section 4.1.5), the subject is lost to follow-up, the subject starts alternative treatment, or the subject is enrolled in another clinical study.

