4.7.2 Prohibited Concomitant Medications

Other than the medications described above, use of concomitant medications or herbal supplements at the times specified in the list below is not permitted. Subjects must be instructed not to take any medications, including over-the-counter products, without first consulting with the investigator.

- Concurrent or previous use of a GLP-1 analogue containing preparation within the last 30 days or 5 half-lives of the drug, whichever is longest, prior to the start of screening (Visit 1)
- Concurrent use of any herbal preparations or medicinal products licensed for control of body weight or appetite and within 1 week prior to the start of the single-blind placebo treatment period (Visit 2)
- Concurrent or previous use of drugs approved for weight loss (eg, orlistat, bupropion naltrexone, phentermine-topiramate, phentermine, lorcaserin) and within the last 30 days or 5 half-lives of the drug, whichever is longest, prior to the start of the single-blind placebo treatment period (Visit 2)

- Concurrent use of opiates, domperidone, metoclopramide, or other drugs known to alter gastric emptying within 2 weeks prior to the start of Visit 2

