3.2 Analysis Populations

The analysis populations are defined in Table 1.

Table 1 Analysis Populations

Population	Description
Intent-to-treat (ITT) population	Subjects who receive any study investigational product will be included in the ITT population and subjects will be analyzed according to their randomized treatment group.
Modified Intent-to-treat (mITT) population	Subjects in the ITT population who receive at least one dose of the investigational product in the double-blind treatment period, and subjects will be analyzed according to their randomized treatment group.
As-treated population	Subjects who receive any study investigational product will be included in the as-treated population and will be analyzed according to the treatment they actually receive.
Per-protocol population	Subjects in the mITT population (receive at least one dose of the investigational product in the double-blind treatment period) who complete treatment up to Day 58.
PK population	Subjects in the As-treated population who have at least one PK sample taken with a value that is above the lower limit of quantitation.
Immunogenicity population	Subjects in the As-treated population who have at least one serum sample for immunogenicity testing.

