3.4.2.3 Secondary Efficacy Analyses

The analysis of the secondary efficacy endpoints will be performed using the mITT population for endpoints comparing MEDI0382 and placebo during the double-blind treatment period. For secondary efficacy endpoints that allow comparison of MEDI0382 and placebo, the endpoints will be analyzed by an ANCOVA model similar to that used for the primary efficacy analysis. Selected secondary endpoints will also be analysed using the Per-protocol population.

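### The Per-protocol set is only a completers' set: it keeps subjects with important deviations, including use of prohibited weight, appetite or gastric-emptying drugs

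*Protocol*

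**What the plan says.** Protocol 4.8.2: "The Per-protocol population will include all subjects in the mITT population who complete treatment with investigational product up to Day 58". SAP Table 1 (section 3.2) uses the same single test, taking mITT subjects "who complete treatment up to Day 58". Neither definition mentions deviations, concomitant drugs or compliance.

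The set has a limited use. SAP 3.4.2.3: "Selected secondary endpoints will also be analysed using the Per-protocol population". The endpoints are not named, and no Per-protocol analysis is planned for the primary endpoint.

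Protocol 4.7.2 states that "use of concomitant medications or herbal supplements at the times specified in the list below is not permitted". The list covers GLP-1 analogues, weight and appetite products, and opiates, domperidone, metoclopramide and other drugs that alter gastric emptying. SAP 3.10 promises a listing and a table of important deviations and gives them no further role.

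**The concern.** A per-protocol analysis is normally run to see whether the main result survives once subjects who departed from the protocol in ways that matter for efficacy are set aside. Here it sets aside only those who stopped treatment early. A subject who takes a prohibited weight, appetite or gastric-emptying drug and keeps injecting stays in both analyses. Agreement between the mITT and Per-protocol results would then say nothing about those drugs.

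This matters more than usual for two reasons. The prohibited drugs act on what the trial measures: body weight, intake at the ad libitum lunch and glucose. And the placebo arm has 8 subjects, so each one carries 12.5% of its mean.

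**Working it through.** **1. Follow one user of a Section 4.7.2 drug through the rules.**

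| Question | Source | Answer |
|---|---|---|
| In mITT? | Protocol 4.8.2: at least one double-blind dose | Yes |
| Does use itself stop investigational product? | Protocol 4.1.6: not listed; noncompliance counts only if the investigator or sponsor judges that it warrants withdrawal | Not by itself |
| In Per-protocol? | Protocol 4.8.2, SAP Table 1: treatment completed to Day 58 | Yes |
| Removed for an important deviation? | SAP 3.10: listing and table only | No |
| Values handled differently? | SAP 3.1, 3.4.1.2, 3.4.2.2: observed data used; LOCF only for missing values | No |
| Term in the model? | SAP 3.4.1.3: treatment and baseline weight | No |

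The two analyses therefore differ only by the non-completers.

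**2. The plan's own figure.** SAP 2.4 gives 16 vs 8 subjects, difference 2.5%, SD 2.0%, two-sided alpha 0.10 and power above 90%.

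Power = Φ(δ / (σ√(1/n₁ + 1/n₂)) − 1.645) = Φ(2.5 / (2.0 × √(1/16 + 1/8)) − 1.645) = Φ(2.887 − 1.645) = 89.3%. The noncentral t with 22 df gives 87.5%. Both are close to the stated figure and slightly below it.

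**3. What a retained user can do (assumed values).** If k of n subjects in an arm are each shifted by e, the arm mean moves by k × e / n.

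- One placebo subject, e = 2 points: 1 × 2 / 8 = 0.25 points, or 10% of 2.5.
- One MEDI0382 subject, e = 2 points: 1 × 2 / 16 = 0.125 points.
- Three placebo subjects, e = −2 to +2: 3 × 2 / 8 = 0.75, so the expected difference is 1.75% to 3.25% (power 64.6% to 98.2%, normal approximation).

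**4. What excluding users would cost.** Power for the 2.5% difference, normal / t:

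| MEDI0382 vs placebo | Power |
|---|---|
| 16 vs 8 | 89.3% / 87.5% |
| 16 vs 7 | 86.7% / 84.7% |
| 14 vs 7 | 85.4% / 83.1% |
| 14 vs 6 | 82.0% / 79.4% |
| 12 vs 6 | 80.4% / 77.3% |

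**5. Why rescue is a different case.** Let the other placebo subjects average m mmol/L, let k of 8 be rescued, let each rescued subject stand at 14 without rescue (the threshold in Protocol 3.1.4.3), and let rescue lower glucose by d. The placebo mean without rescue is m + k(14 − m)/8. Keeping rescued subjects understates it by k × d/8. Excluding them understates it by k(14 − m)/8. With m = 9 and d = 3 to 5, all assumed:

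| Rescued | Mean without rescue | Kept | Excluded |
|---|---|---|---|
| 1 of 8 | (7×9 + 14)/8 = 9.63 | 9.25 to 9.00 | 9.00 |
| 2 of 8 | (6×9 + 2×14)/8 = 10.25 | 9.50 to 9.00 | 9.00 |

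Exclusion does better only when d exceeds 14 − m. At m = 9 that never happens in this range. For m between 9 and 11 it depends on d, and only above 11 does exclusion win throughout.

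**6. Can the Section 4.7.2 test be applied as written?** Not fully. The weight, appetite and GLP-1 items cover concurrent use. The gastric-emptying item ties concurrent use to a two-week window before Visit 2, while Section 4.7.1 permits anti-emetics and analgesics as classes unless Section 4.7.2 excludes them. Whether metoclopramide, domperidone or an opiate taken after Day 17 is a deviation cannot be settled from the text.

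**The case against.** Using all data whatever else was taken is a legitimate treatment-policy analysis, and this is a 24-subject exploratory study without multiplicity control. That stands, and it is the reason to leave mITT alone. It does not explain a second set that handles these subjects identically.

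The definition does not itself affect the primary endpoint, since Per-protocol serves only selected secondary endpoints. That also stands. Adding percentage weight change to the set is a new supportive analysis, not the correction of a planned one.

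SAP 3.3.4 already summarises concomitant drugs by treatment and separately for the double-blind period, and SAP 3.10 tabulates important deviations. These show that use occurred but not what it did to the results. Some noncompliant subjects may also be stopped by judgement and so leave the set; that is possible but not assured.

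A reader might go further and infer that rescued subjects are the main problem, that rescue will fall mostly on placebo, and that excluding them would isolate the drug effect. Only part of this has support. Rescue is foreseen ("the investigator should consider rescue therapy following discussion with the medical monitor"), and the listed ground for stopping product is glucose that stays high "despite a maximum tolerated dose of rescue therapy", so a rescued subject normally does remain per-protocol. But the documents give no rate. Entry requires HbA1c of at most 8.0%, metformin continues, the laboratory route needs at least two fasting values above 14 mmol/L more than 3 days apart, and double-blind treatment lasts 42 days. More rescue on placebo is a reasonable inference from the glucose hypothesis in Protocol 1.7.2, not a stated fact. And exclusion removes the placebo subjects with the worst glycaemia, which can shrink the difference as much as keeping them.

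**Conclusion.** The point holds in a limited form. The Per-protocol set is a completers' set in both documents, and no readable text links an important deviation or prohibited-drug use to it. The supportive analysis therefore cannot show whether such drugs affected weight, energy intake or glucose.

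The size cannot be derived from the documents. On an assumed 2-point weight shift, each retained placebo user moves that arm's mean by 0.25 points against a design difference of 2.5. With few or no users the effect is negligible. This is an inexpensive correction to a supportive analysis and does not challenge the mITT primary result.

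Two limits apply. The treatment-compliance and exploratory-analysis sections are blacked out and the programming plan is not supplied, so the absence of a planned analysis is established for the readable text only. And the documents do not support treating exclusion of rescued subjects as the remedy.

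**What to change.** - **Definition.** In Protocol 4.8.2 and SAP Table 1, define Per-protocol as mITT subjects who complete treatment to Day 58 and have no important protocol deviation likely to affect efficacy. Count concurrent use of a Section 4.7.2 drug in the double-blind period as one such deviation.
- **Exclusion list.** Fix it by blinded review before unblinding. First reconcile Protocol 4.7.1 with 4.7.2 on which on-treatment anti-emetic, analgesic or gastric-emptying drug use is prohibited; that decision belongs to the protocol's authors.
- **Endpoints.** Name those to be analysed in this set, and add percentage weight change from Day 17 to 59 as a supportive analysis.
- **Rescue.** Do not exclude rescued subjects as a way to isolate the drug effect. Flag rescue by arm in the concomitant-medication summary. If any occurs, add a supplementary fasting-glucose analysis using the last laboratory value before rescue. Such values are selected for being high, so read that analysis alongside mITT, not in place of it.

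The cost is wording in two documents and a blinded review of records already collected. The set may lose a few subjects (power as in the table above), and the replacement rule in Protocol 4.1.7 covers withdrawals from the study, not exclusions from this set. Because the set is selected after randomisation it must stay supportive. The mITT analysis does not change.

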4.8.3 Sample Size

[REDACTED]

4.8.4 Efficacy

4.8.4.1 Primary Efficacy Analysis

The efficacy analysis will be based on the mITT population. The primary efficacy endpoint of percentage change in body weight from Day 17 to 59 will be compared between MEDI0382 and placebo groups using an analysis of covariance (ANCOVA) model adjusting for treatment group and measurement at baseline. Last observation carried forward will be used for missing data imputation for post-baseline values when applicable.

4.8.4.2 Secondary Efficacy Analyses

The secondary efficacy endpoints will be based on the mITT population and analysed by an ANCOVA model similar to that used for the primary efficacy analysis. Selected secondary endpoints will also be analysed using the Per-protocol population.

4.8.4.3 Exploratory Efficacy and Pharmacodynamic Analyses

4.8.5 Safety

4.8.5.1 Analysis of Adverse Events

The safety analysis will be based on the As-treated population. Adverse events and SAEs will be coded by the most updated version of the Medical Dictionary for Regulatory Activities (MedDRA) and the type, incidence, severity, and relationship to investigational product by will be summarized by MedDRA System Organ Class (SOC) and Preferred Term (PT). Specific AEs will be counted once for each subject for calculating percentages. In addition, if the same AE occurs multiple times within a particular subject, the highest severity and level of relationship observed will be reported. All TEAEs will be summarized overall, by MedDRA SOC and PT, and by severity and relationship to investigational product. In addition, summaries of deaths, SAEs, and treatment discontinuations due to AEs will be provided.

4.8.5.2 Analysis of Clinical Laboratory Parameters

Additional safety data including vital signs, safety laboratory analysis, and ECGs will be summarised descriptively at each time point by treatment group.

4.8.6 Analysis of Immunogenicity

4.8.7 Analysis of Pharmacokinetics

4.8.8 Patient Reported Outcomes

Analysis of patient reported outcomes (PROs) will be based on the mITT population. The exploratory PRO endpoints including change in self-reported hunger and satiety scores from, Day 15 to 58 and the change in total energy intake in kilojoules (kJ) as recorded in a food diary from Day 16 to 32 and from Day 16 to 59 will be analysed by an ANCOVA model similar to that used for the primary efficacy analysis.

4.8.9 Interim Analysis

No interim analyses are planned.

5 ASSESSMENT OF SAFETY

5.1 Definition of Adverse Events

The ICH Guideline for Good Clinical Practice E6(R1) defines an AE as:

Any untoward medical occurrence in a patient or clinical investigation subject administered a pharmaceutical product and which does not necessarily have a causal relationship with this treatment. An AE can therefore be any unfavourable and unintended sign (including an abnormal laboratory finding), symptom, or disease temporally associated with the use of a medicinal product, whether or not considered related to the medicinal product.

An AE includes but is not limited to any clinically significant worsening of a subject's pre-existing condition. An abnormal laboratory finding (including ECG finding) that requires medical intervention by the investigator, or a finding judged by the investigator as medically significant should be reported as an AE. If clinical sequelae are associated with a laboratory abnormality, the diagnosis or medical condition should be reported (eg, renal failure, haematuria) not the laboratory abnormality (eg, elevated creatinine, urine red blood cell increased). Abnormal laboratory values that are not, in the investigator's opinion, medically significant and do not require intervention should not be reported as AEs.

AEs may be treatment emergent (ie, occurring after initial receipt of investigational product) or nontreatment emergent. A nontreatment-emergent AE is any new sign or symptom, disease, or other untoward medical event that begins after written informed consent has been obtained but before the subject has received investigational product.

Elective treatment or surgery or preplanned treatment or surgery (that was scheduled prior to the subject being enrolled into the study) for a documented pre-existing condition that did not worsen from baseline is not considered an AE (serious or nonserious). An untoward medical event occurring during the prescheduled elective procedure or routinely scheduled treatment should be recorded as an AE or serious adverse event (SAE).

5.2 Definition of Serious Adverse Events

An SAE is any AE that:

- Results in death
- Is immediately life-threatening
- Requires inpatient hospitalization or prolongation of existing hospitalization
- Results in persistent or significant disability/incapacity
- Is a congenital anomaly/birth defect in offspring of the subject
- Is an important medical event that may jeopardize the subject or may require medical intervention to prevent one of the outcomes listed above

Medical or scientific judgment should be exercised in deciding whether expedited reporting is appropriate in this situation. Examples of medically important events are intensive treatment in an emergency room or at home for allergic bronchospasm, blood dyscrasias, or convulsions that do not result in hospitalizations; or development of drug dependency or drug abuse.

5.3 Recording of Adverse Events

AEs will be recorded on the eCRF using a recognized medical term or diagnosis that accurately reflects the event. AEs will be assessed by the investigator for severity, relationship to the investigational product, possible etiologies, and whether the event meets criteria of an SAE and therefore requires immediate notification to the sponsor (Section 5.4). See Section 5.2 for the definition of SAEs and Section 10.3 for guidelines for assessment of severity and relationship.

If an AE evolves into a condition that meets the regulatory definition of ‘serious’, it will be reported on the SAE Report Form.

5.3.1 Time Period for Collection of Adverse Events

AEs and SAEs will be collected from time of signature of informed consent throughout the study including the follow-up period as described above.

5.3.2 Follow-up of Unresolved Adverse Events

Any AEs that are unresolved at the subject's last visit in the study are followed up by the investigator for as long as medically indicated, but without further recording in the eCRF. MedImmune retains the right to request additional information for any subject with ongoing AE(s)/SAE(s) at the end of the study, if judged necessary. Updates regarding SAEs that were ongoing at the time of the subject's completion of study participation should be submitted to the study representative using a paper SAE follow-up form.

5.3.3 Deaths

All deaths that occur during the study, including the protocol-defined follow-up period must be reported as follows:

- An AE causing the death must be reported as an SAE within 24 hours. The report should assign main and contributory causes of death.
- Deaths with an unknown cause should always be reported as an SAE. A post-mortem (autopsy) may be helpful in the assessment of the cause of death, and if performed a copy of the post-mortem results should be forwarded to the sponsor representative(s) within the usual timeframes (refer to Section 5.4 for additional information).

5.4 Reporting of Serious Adverse Events

All SAEs have to be reported, whether or not considered causally related to the investigational product, or to the study procedure(s). All SAEs will be recorded in the CRF.

If any SAE occurs in the course of the study, then investigators or other site personnel must inform the appropriate sponsor representative(s) within 1 day, ie, immediately but no later than 24 hours after becoming aware of the event.

The designated sponsor representative works with the investigator to ensure that all the necessary information is provided to the sponsor's patient safety data entry site within 1 calendar day of initial receipt for fatal and life-threatening events and within 5 calendar days of initial receipt for all other SAEs.

For fatal or life-threatening AEs where important or relevant information is missing, active follow-up is undertaken immediately. Investigators or other site personnel inform sponsor representatives of any follow-up information on a previously reported SAE within 1 calendar day, ie, immediately but no later than 24 hours after becoming aware of the event.

Once the investigators or other site personnel indicate an AE is serious in the electronic data capture (EDC) system, an automated email alert is sent to inform the designated sponsor representative(s).

If the EDC system is not available, then the investigator or other study site personnel reports an SAE to the appropriate sponsor representative by telephone. The sponsor representative will advise the investigator/study site personnel how to proceed.

